23 ASSESSMENTS

23.1 Efficacy Assessments.

Efficacy assessment will be based on the categorical measure of a Responder, defined as the proportion of subjects at Day 60 post-dosing in each active dose group compared to placebo with a 50% or greater improvement in Mean Worst Daily Leg Pain (WDLP) score compared to baseline. This pain scoring data will be derived from the E-Diary recordings entered by the subjects using eREsearch Technologies Inc electronic Clinical Outcome Assessment SALIENT Clinical Study app (ERT LPRI 424/301). WDLP score will be collected via the app once daily between 18:00:00 and 23:59:59 using the prompt *What was your worst leg pain today?* and a visual scoring range of 0 (no leg pain) to 10 (worst imaginable leg pain).

Subjects will be trained and reminded at each study visit to enter a measure of worst daily leg pain in the evening of each day. This is to establish a learned behaviour that ensures appropriate recording of the essential time period from which the mean values are derived. Where WDLP score has not been entered into the SALIENT Clinical Study app for a given 24hour period, an email notification will be automatically sent to the study team to follow up with the subject to ensure ongoing compliance to submission of WDLP data. The mean WDLP will be calculated as defined further below.

It is important that the critical levels of Mean Worst Daily Leg Pain (NRS Score of 5.0-9.0) is *NOT communicated to the patient at any stage* so that they remain unprogrammed and objective in any daily scoring.

The information contained in this document is the property of SpineThera Australia Pty Ltd and may not be reproduced, published or disclosed to others without written authorization.

CLINICAL PROTOCOL

Sponsor: SpineThera Australia Pty Ltd

CLIN-0012-STA01-19 Revision: 06
Effective Date: 17 Jun2020

Page: 55 of 76

If, in the opinion of the Investigator, additional treatment beyond the rescue medication approach provided in this protocol is required, for example surgery, the patient will be deemed a non-responder in the efficacy analysis at timepoints after the additional treatment but will continued to be followed in the safety population. In this case, the patient shall not continue to report worst daily leg pain score in the electronic diary but shall continue to record concomitant therapy and safety measures in the paper diary.

[REDACTED]

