25.8 Treatment of Subjects

25.8.1 Rescue Medication

All subjects entering this study are required to keep all analgesic medication and other therapy usage [such as physiotherapy, acupuncture, or TENS] stable or decreased during the study, and only use the rescue pain medication as needed and specified by the protocol.

If pain control is unsatisfactory, the Investigator has a range of Rescue medications that can be added to the maintenance therapy that the subject takes as concomitant medications.

Any one of the Group 1 and/or any one of the Group 2 rescue medications are available for increases in pain for selection and prescription by the Investigator for up to 14 days (once during the study) as addition

The information contained in this document is the property of SpineThera Australia Pty Ltd and may not be reproduced, published or disclosed to others without written authorization.

CLINICAL PROTOCOL

Sponsor: SpineThera Australia Pty Ltd

CLIN-0012-STA01-19 Revision: 06
Effective Date: 17 Jun2020

Page: 64 of 76

to the medications currently used by the patient, with special consideration of safety and potential drug interactions.

Group 1 (one of):

- Amitriptyline 5 – 50mg Nocte, *or*
- Pregabalin 25mg – 300mg BD, *or*
- Gabapentin 100mg TDS dosage, up to 600mg TDS

(Acute withdrawal of gabapentin or pregabalin can result in withdrawal symptoms, with likelihood of withdrawal related to dose and duration of treatment. If appropriate, down-titration should take place over at least one week, starting no later than day 15 after rescue began.)

and/or Group 2 (one of):

- Tramadol 100mg – 200mg BD, *or*
- Tapentadol 50 – 200mg BD

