7.1 Primary Efficacy Endpoint and Analyses

Efficacy assessments will be based on the categorical measure of 50% Responder, defined as a patient with 50% or greater improvement in mean Worst Daily Leg Pain (WDLP) score compared to baseline. The mean WDLP score will be derived from the E-Diary recordings entered by the subjects, [REDACTED]

[REDACTED]

[REDACTED]

[REDACTED]

[REDACTED]

[REDACTED]

[REDACTED]

Incomplete Mean Worst Daily Leg Pain score:

All subjects with 5 or more Worst Daily Leg Pain scores recorded in the 10 days preceding the study visit will be included in the analysis. If a subject has less than 5 scores preceding a visit, the subject will not be included in the efficacy assessment for that particular visit. If that same subject has provided 5 or more scores in the 10 days preceding a later visit, the subject will be included in the efficacy assessment for the later visit.

Early Withdrawal:

If a subject withdraws from the study before their 180 day visit, the subject will be included in analyses up to the time that they either stop attending follow-up visits or their consent was withdrawn.

Rescue Medication:

If a patient has failed rescue medication (defined as taking rescue medication for >14 days, taking rescue medication in more than one episode, or receiving treatment beyond the rescue medication regimen defined in the protocol

then the patient will be deemed a non-responder at all timepoints after exceeding the allowed rescue medication, on the day the second episode of Rescue Medication began, or after receiving the additional treatment. The patient will be included in all subsequent timepoints as a non-responder, whether withdrawn or not.

7.1.1 Mean Worst Daily Leg Pain Score: Proportion of Patients with 50% or Greater Improvement from baseline at 60 Days Post-Dosing (Primary Endpoint)

The number and percentage of patients experiencing a 50% or greater improvement from baseline in mean Worst Daily Leg Pain score (i.e. the number and percentage of 50% Responders) will be tabulated for each treatment group. The primary analysis will descriptively compare the proportions of 50% Responders in each of the three arms. The “study success” criterion is defined as the observed percentage of 50% Responders in the high dose group being at least 10 percentage points greater than the corresponding rate in the placebo group.

Listings of Worst Daily Leg Pain will be provided for the modified intent-to-treat population.

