7.2.2 Change from Baseline in Mean Worst Daily Leg Pain Score

A graphical display of mean observed Daily Leg Pain values over time by treatment group for the mITT population will be prepared.

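### Read literally, the pain diary stops when further treatment is judged necessary but failure counts only once it is given, so a waiting patient can drop out of the Day 60 analysis

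*Protocol*

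**What the plan says.** Protocol 23.1 opens the rule with a condition about need: "If, in the opinion of the Investigator, additional treatment beyond the rescue medication approach provided in this protocol is required, for example surgery". It dates the consequence from something else: "the patient will be deemed a non-responder in the efficacy analysis at timepoints after the additional treatment". The next sentence deals with data collection: "In this case, the patient shall not continue to report worst daily leg pain score in the electronic diary". Concomitant therapy and safety recording go on in the paper diary. Section 23.5.5 repeats the non-responder timing.

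SAP 7.1 (version 1.1) has three triggers for failed rescue. Two concern the amount of rescue used: "defined as taking rescue medication for >14 days, taking rescue medication in more than one episode". The third concerns receipt: "or receiving treatment beyond the rescue medication regimen defined in the protocol". Non-response then starts after the rescue allowance is exceeded, "on the day the second episode of Rescue Medication began, or after receiving the additional treatment". From that point the SAP counts the patient as a failure at every later visit, even after withdrawal.

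SAP 7.1 also requires at least five diary scores in the 10 days before a visit; a patient with fewer is left out of that visit's efficacy assessment. SAP 5.9 refers elsewhere for the primary endpoint and otherwise allows no imputation. For pain intensity, SAP 7.2.2 says: "A graphical display of mean observed Daily Leg Pain values over time by treatment group for the mITT population will be prepared".

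**The concern.** Two clocks run for one event. On the literal reading, scoring ends at the judgement that more treatment is needed, while failure is dated from the day that treatment is given. Between the two, the patient is still in the study and may attend visits, but has no scores because the protocol ended them, and is not yet a non-responder. If that interval spans the Day 60 visit, the minimum-score rule removes the patient from the denominator. That works against the SAP's own aim of carrying rescue failures forward as non-responders.

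The primary result is judged on an observed difference of at least 10 percentage points between high dose and placebo, in a trial stopped at 55 patients. One or two patients moving in or out of a denominator can matter.

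The curve raises a second issue. Once additional treatment has been given, the diary instruction ends scoring under any reading, so those patients leave a display built from observed values. The visible text has no such stop for patients who fail by prolonged or repeated rescue, so failures are handled differently according to type.

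**Working it through.** **The plan's own figure.** Protocol 31.2 and SAP 3.3 state 94% power (50% vs 20%) and 81% (50% vs 25%) with 60 per arm, two-sided 0.05. With the pooled z formula, power = Φ[(|p1 − p2| − 1.96·√(2p̄(1 − p̄)/n)) / √(p1(1 − p1)/n + p2(1 − p2)/n)]:
- 50% vs 20%: (0.300 − 0.171)/0.0827 = 1.56, power 94.1%.
- 50% vs 25%: (0.250 − 0.173)/0.0854 = 0.90, power 81.6%.

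Both agree with the plan. The point here rests on a classification rule and not on this calculation.

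**When a stopped diary removes a visit.** One score per day (protocol 23.1), a 10-day window and a minimum of five scores (SAP 7.1). With full compliance up to the stop, a diary stopped g days before the visit leaves 10 − g scores.
- g = 5: 5 scores, so the patient is classified from the scores.
- g = 6: 4 scores, so the patient is left out unless a SAP trigger has been met.

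Example (dates assumed): judged to need surgery on Day 40, operated on Day 100, neither rescue limit passed and no other treatment beyond rescue received. There are no scores in the 10 days before Day 60 or Day 90, and non-response has not begun, so both visits are lost.

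**Effect on the success criterion.** 55/3 = 18.3, so 18 per arm is assumed. Responder counts and numbers waiting are also assumed; the documents give neither. A waiting failure that is left out reduces the denominator only.

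| Responders, high dose / placebo | All failures counted | Left out | Difference in points | 10-point criterion |
|---|---|---|---|---|
| 8 / 6 | 11.1, met | 1 placebo | 8/18 − 6/17 = 44.44 − 35.29 = 9.2 | not met |
| 6 / 4 | 11.1, met | 1 placebo | 6/18 − 4/17 = 33.33 − 23.53 = 9.8 | not met |
| 8 / 7 | 5.6, not met | 2 high dose | 8/16 − 7/18 = 50.00 − 38.89 = 11.1 | met |
| 6 / 5 | 5.6, not met | 2 high dose | 6/16 − 5/18 = 37.50 − 27.78 = 9.7 | not met |
| 6 / 5 | 5.6, not met | 3 high dose | 6/15 − 5/18 = 40.00 − 27.78 = 12.2 | met |
| 9 / 4 | 27.8, met | 3 high dose | 9/15 − 4/18 = 60.00 − 22.22 = 37.8 | met |
| 9 / 4 | 27.8, met | 3 placebo | 9/18 − 4/15 = 50.00 − 26.67 = 23.3 | met |

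Losses in the high-dose arm enlarge the difference; losses in the placebo arm shrink it. Only the near-threshold cases flip.

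**Effect on the curve.** Suppose 15 of 18 patients score 4 and 3 would have scored 8 but have stopped. The mean over all is (15×4 + 3×8)/18 = 84/18 = 4.67; the displayed mean is 4.00. The scores are assumptions. If the missing scores were below 4, for instance after successful surgery, the shift would go the other way.

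**The case against.** The main counter-argument is textual. The diary sentence follows a clause about a patient who has already had the additional treatment, and its opening words can refer to that patient. Diary stop and non-response would then start together and no Day 60 gap would arise. This is a possible reading. The judgement is the more literal one, because it is the condition that opens the rule, and sites need one date. The curve issue survives either way.

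Second, a reader might infer that every waiting patient lacks a Day 60 status, or that failure can begin only on receipt of the new treatment. The documents do not support that. More than 14 days of rescue or a second episode already makes the patient a non-responder, as does receiving any treatment beyond the rescue regimen, not only surgery. A diary stopped within five days of the visit can still leave five scores. The gap is confined to patients outside all of these.

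Third, redaction falls beside the rule. Protocol 23.1 is blacked out just after the diary sentence, parts of SAP 7.1 are hidden, and no content of SAP 7.3 is visible. SAP version 1.0 shows the tail of a derivation rule concerning treatment beyond rescue, and the version 1.1 change log does not mention its removal. A covering rule cannot be excluded; this stands as a limit on the conclusion.

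Fourth, ending scores after additional treatment fits a responder endpoint that already counts those patients as failures. That is reasonable for the responder endpoint, but it does not help a curve of observed scores.

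**Conclusion.** The inconsistency is real and worth correcting, within limits. On the visible text read literally, a patient judged to need treatment beyond rescue but not yet given it, who has met neither rescue-use trigger and whose diary stopped six or more days before the visit, is left out of the Day 60 responder analysis instead of counting as a failure. Under the assumptions above, one such placebo patient, or two to three in the high-dose arm, can flip the 10-point criterion when the result is close; at 9/18 vs 4/18 up to three in either arm do not. How many patients are affected is unknown, and no direction of bias can be claimed in advance.

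The observed-score curve loses patients after additional treatment under either reading. A reader might go further and say that it loses the worst patients, that it is the only comparison of pain between arms, or that nothing can be recovered. The first is a plausible inference but not documented. The second is wrong: SF-36 bodily pain is summarised by arm at each visit (SAP 7.2.5). The third is true of uncollected scores only; responder status can be corrected by reclassification if the judgement date is on record.

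**What to change.** 1. Reconcile protocol 23.1, 23.5.5 and SAP 7.1 so that, for analysis, non-responder status starts on the recorded date of the Investigator's judgement, or on receipt of the treatment if earlier. This needs one date on the CRF, or retrieved from source records, and a wording change. It also works for follow-up already completed wherever the date was recorded.
2. Delete the instruction to stop the electronic diary for patients who remain in the study. The cost is a continued once-daily app entry and a protocol amendment with sponsor and ethics approval. Enrolment has ended, so this helps only follow-up still to come.
3. In SAP 7.2.2, show the number contributing by arm and visit beneath the curve, and identify scores recorded after additional treatment.
4. If a redacted rule already covers the interval between judgement and treatment, cite it in all three places.

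These changes concern data collection and classification for analysis only; no clinical rule is proposed.

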23.2 Functional Outcomes

Functional outcomes following treatment will be assessed by the Oswestry Low Back Pain Disability Questionnaire (Oswestry Disability Index) which provides information as to how the pain has affected the subject's ability to manage everyday life. This test has been in use since 1980 and is considered a "gold standard" of low back pain functional outcome tools. The Questionnaire will be completed by the subject at each study visit. The Disability Index will be calculated from each completed Questionnaire by the study personnel.

Interpretation of scores is:

- 0% to 20%: minimal disability
- 21% to 40%: moderate disability
- 41% to 60%: severe disability
- 61% to 80%: crippling back pain
- 81% to 100%: these subjects are either bed-bound or exaggerating their symptoms

23.3 Patient Clinical Global Impression of Change

A Patient Clinical Global Impression of Change will be assessed using the following 7-point scoring classification:

The information contained in this document is the property of SpineThera Australia Pty Ltd and may not be reproduced, published or disclosed to others without written authorization.

CLINICAL PROTOCOL

Sponsor: SpineThera Australia Pty Ltd

CLIN-0012-STA01-19 Revision: 06
Effective Date: 17 Jun2020

Page: 56 of 76

1. Very much improved
2. Much improved
3. Slightly improved
4. No change
5. Slightly worse
6. Much worse
7. Very much worse

23.4 SF-36 Assessments

SF-36 is a set of generic, coherent, and easily administered quality-of-life measures., presented as a questionnaire that addresses eight health concepts:

- physical functioning (PF)
- role physical (RP)
- bodily pain (BP)
- general health (GH)
- vitality (V)
- social functioning (SF)
- role emotional (RE)
- mental health (MH)

The Quality of Life patient questionnaire Short Form (36) Health Survey (SF-36) will be completed by patients at each visit.

23.5 Safety Assessments

23.5.1 Adverse Events

Adverse events, including Serious Adverse Events will be collected throughout the study duration, starting at Visit 2 (Baseline/Treatment, Day 0) and ending at Visit 9 (Day 180 post-dosing) or until all ongoing adverse events are deemed resolved or stable by the Principal Investigator. Where an early withdrawal visit occurs prior to Visit 4, the Investigator must report all SAEs occurring from the time of Visit 2 (Baseline/Treatment) until 30 days after treatment with the IMP/Placebo.

Resolution of an AE is defined as the return to pre-treatment status or stabilization of the condition with the expectation that it will remain chronic.

Adverse events will be reported by the study subjects in the subject diary and/or to the study staff at each study visit. Recording of AEs will occur on an Adverse Event eCRF which will include the reported verbatim term (diagnosis where possible), Start Date, End Date, Outcome, Severity, Causality, Action Taken with IP and procedure and Seriousness.

Any SAE or subject death that occurs from and including Visit 2 (Baseline/Treatment onwards, whether or not related to IMP/Placebo, must be reported within 24 hours via e-mail at the address noted below. A completed Serious Adverse Event Report Form with as much detail as possible must be included with the email, while ensuring that the SAE report contains the minimum criteria for reporting (participant ID, adverse event term, suspected investigational product, reason for meeting serious criteria and relationship to investigational product, name of the reporter).

Contact Information for SAE Reporting

CLINICAL PROTOCOL

Sponsor: SpineThera Australia Pty Ltd

CLIN-0012-STA01-19 Revision: 06
Effective Date: 17 Jun2020

Page: 57 of 76

Pre-existing conditions or planned treatment (such as hospitalization) for pre-existing conditions are not considered adverse events unless the nature and severity of the condition has worsened.

Details of AE definitions, collection, recording, and reporting are found in Section 26.2

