13.3 Procedural Relative Contraindications (SIS practice guidelines)

- Allergy to any of the drugs that are to be administered.
- Pregnancy
- Concurrent use of anticoagulants
- Anatomical derangements, congenital or surgical, that compromise the safe and successful conduct of the procedure
- Known systemic infection
- Coexisting disease producing significant respiratory or cardiovascular compromise
- Immunosuppression

Risks include but are not limited to infection, allergic reaction, haematoma, no change in pain or increased pain, dural puncture with spinal headache or arachnoiditis, and spinal cord injury. The subject should be fully informed and should understand what to expect: that they might experience numbness

CLINICAL PROTOCOL

Sponsor: SpineThera Australia Pty Ltd

CLIN-0012-STA01-19 Revision: 06
Effective Date: 17 Jun2020

Page: 32 of 76

or weakness in the lower limb following the procedure. This is a normal effect of the local anaesthetic that is injected, and it should wear off once the local anaesthetic has ceased to act.

[REDACTED]

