26.1 Adverse Event Definitions

Adverse events will be defined by the NHMRC Guidance: Safety monitoring and reporting in clinical trials involving therapeutic goods (November 2016).

Table 7. Adverse Event Definitions.

Seriousness	
Adverse event (AE)	Any untoward medical occurrence in a patient or clinical trial participant administered a medicinal product and that does not necessarily have a causal relationship with this treatment.
Adverse reaction (AR)	Any untoward and unintended response to an investigational medicinal product related to any dose administered.
Safety Critical Adverse Events	Adverse events and/or laboratory abnormalities identified in the protocol as critical to safety evaluations that should be reported to the sponsor according to the reporting requirements specified in the protocol.
Serious Adverse Event (SAE)/Serious Adverse Reaction (SAR)	Any adverse event/adverse reaction that results in death, is life-threatening, requires hospitalisation or prolongation of existing hospitalisation, results in persistent or significant disability or incapacity, or is a congenital anomaly or birth defect.
Significant Safety Issue (SSI)	A safety issue that could adversely affect the safety of participants or materially impact on the continued ethical acceptability or conduct of the trial.
Urgent Safety Measure (USM)	A measure required to be taken in order to eliminate an immediate hazard to a participant's health or safety.
Severity	
Mild	event requires minimal or no treatment and does not interfere with the participant's daily activities
Moderate	event results in a low level of inconvenience or concern with the therapeutic measures. Moderate events may cause some interference with functioning.
Severe	event interrupts a participant's usual daily activity and may require systemic drug therapy or other treatment. Severe events are usually incapacitating.
Life-threatening	event in which the subject was at risk of death at the time of the event*
Fatal	event that resulted in death
Causality	
relatedness to IMP/Placebo or relatedness to TF-EI procedure	
Definitely related	There is a reasonable possibility that the IMP/Placebo or the TF-EI procedure caused the AE. Reasonable possibility means that there is evidence to suggest a causal relationship between the IMP/Placebo or the TF-EI procedure and the adverse event.
Probably related	
Possibly related	

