The information contained in this document is the property of SpineThera Australia Pty Ltd and may not be reproduced, published or disclosed to others without written authorization.

CLINICAL PROTOCOL

Sponsor: SpineThera Australia Pty Ltd

CLIN-0012-STA01-19 **Revision: 06**
Effective Date: 17 Jun2020

Page: 66 of 76

Not related	There is not a reasonable possibility that the IMP/Placebo or the TF-EI procedure caused the adverse event
Expectedness	
Suspected Unexpected Serious Adverse Reaction (SUSAR)	An adverse reaction that is both serious and unexpected.
Unexpected Adverse Reaction (UAR)	An adverse reaction, the nature or severity of which is not consistent with the Reference Safety Information (RSI)

Life-threatening in the definition of a serious adverse event or serious adverse reaction refers to an event in which the subject was at risk of death at the time of the event. It does not refer to an event that hypothetically might have caused death if it were more severe.

Medical and scientific judgement should be exercised in deciding whether an adverse event/ reaction should be classified as serious in other situations. Important medical events that are not immediately life-threatening or do not result in death or hospitalisation but may jeopardise the subject or may require intervention to prevent one of the other outcomes listed in the definition above should also be considered serious.

If there is any doubt as to whether a clinical observation is an AE, the event should be reported. All AEs must be assessed for seriousness, severity, relatedness, expectedness and timing by a study Investigator (who is also a clinician). All changes to an AE must be documented. AEs characterized as intermittent require documentation of onset and duration of each episode.

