27 STUDY SUSPENSION OR EARLY TERMINATION

Suspension is a temporary pause in study activities. Early termination is the closure of the study prior to the defined endpoint. Suspension or early termination can occur either at an Investigational Site or across the entire study and may be at the direction of the Sponsor, the HREC or the Regulatory Authority.

Reasons for suspension or early termination of the study may include, but are not limited to, the following:

- Incidence or severity of adverse events represent a significant medical risk. Severity of adverse events will be determined per Table 9: Adverse Event Definitions Specifically, but not limited to:
 - three or more subjects experience the same serious adverse event as evaluated by a licensed clinician.
 - three or more subjects who received one treatment dose experience a severe, treatment-related laboratory abnormality in the same laboratory parameter.
 - an overall pattern of symptomatic, clinical, or laboratory events that the Safety Review Committee consider to be associated with IMP and that may collectively represent a serious potential concern for safety.
- An issue relating to IMP manufacturing or distribution.
- Failure to obtain Human Research Ethics approval or HREC annual report acknowledgement for the study.
- Failure of the Investigator/Investigational Site to comply with the protocol, the Clinical Trial Research Agreement or applicable regulatory guidelines in conducting the study.
- Failure of the Investigator/Investigational Site to accurately and completely collect and record study related data as per GCP.

In the case of study suspension, it is the responsibility of the Sponsor to notify all Investigators and the Human Research Ethics Committee, including the reason for suspension. It is the responsibility of the Investigator to ensure enrolment and treatment (IMP/Placebo administration) of subjects ceases immediately and until the suspension is lifted by the Sponsor and acknowledged by the Human Research Ethics Committee. Enrolled *and* treated subjects will continue to be managed per protocol.

In the case of termination, it is the Sponsor's responsibility to notify all Investigators, the Regulatory Authority and Human Research Ethics Committee immediately, including the reason for termination. It is the Investigator's responsibility to inform the subjects and ensure appropriate care and follow-up is provided.

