9.1 Adverse Events

Adverse events (AEs) will be recorded from the treatment date until the end of study. AEs will also be assessed for seriousness, severity relatedness, and expectedness. AEs will be considered treatment-emergent if their onset occurs within the on-therapy period. Any missing severity assessments will be assumed to be severe, missing relationship assessments will be assumed to be related, and missing seriousness assessments will be assumed as serious.

An overview of treatment-emergent AEs (TEAEs) will be produced, including counts and percentages of patients with any incidences of: TEAEs, TEAEs related to study treatment (i.e., either definitely, probably, or possibly related), TEAEs related to TF-EI procedure (i.e., either definitely, probably, possibly related or not related), severe or worse adverse events (i.e., either severe, life-threatening, or fatal), TEAEs leading to study withdrawal, serious adverse events (SAEs), and fatal SAEs.

Adverse events will be coded based on the Medical Dictionary for Regulatory Affairs (MedDRA) for reporting by system organ class (SOC) and preferred term (PT) in descending order of overall incidence. For these summaries, patients will be counted once within each SOC and PT.

Summaries of adverse events by SOC and PT will include the following types:

- TEAEs;
- TEAEs related to study treatment (including definitely, probably, or possibly related events, and events with missing relatedness);
- TEAEs related to TF-EI procedure (including definitely, probably, or possibly related events, and events with missing relatedness);
- Severe or worse TEAEs (including severe, life-threatening, or fatal events, and events with missing severity);
- SAEs; and
- TEAEs leading to study withdrawal;

A summary of TEAEs by SOC, PT, and maximum severity will also be prepared. Maximum severity will be based on the following scales:

- Fatal
- Life-Threatening
- Severe
- Missing

Sponsor: SpineThera Australia Pty. Ltd

Protocol Number: CLIN-0012-STA01-19

SAP Version and Date: Amendment Final 1.1, 13JUL2022

- Moderate
- Mild

A comprehensive listing of all AEs will be provided in a by-patient data listing. In addition, the following listings will be provided:

- TEAEs related to study treatment (including definitely, probably, or possibly related events, and events with missing relatedness);
- SAEs;
- TEAEs leading to study withdrawal; and
- Fatal AEs.

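### Read literally, Protocol 23.5.1 does not count severity-only worsening of a pre-existing condition as an adverse event; this conflicts with Section 26.1, and the SAP does not repair it

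*Protocol*

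**What the plan says.** Protocol 23.5.1 (Revision 06) states that pre-existing conditions, and planned treatment for them such as a hospital stay, "are not considered adverse events unless the nature and severity of the condition has worsened". It refers the reader to Section 26.2 for detail. It also treats a return to the pre-treatment state as resolution of an event.

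Table 7 in Protocol 26.1 defines an adverse event as "Any untoward medical occurrence in a patient or clinical trial participant administered a medicinal product", whether or not treatment caused it, and makes no exception for conditions present at entry. The text after the table adds: "If there is any doubt as to whether a clinical observation is an AE, the event should be reported". A serious adverse event must first be an adverse event or reaction: "Any adverse event/adverse reaction that results in death, is life-threatening, requires hospitalisation or prolongation of existing hospitalisation", or one of the other listed outcomes. Protocol 31.7 likewise builds treatment-emergent events (TEAEs) from adverse events.

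Protocol 13.3 names "no change in pain or increased pain" among the risks of the procedure. One of the reasons for suspension in Protocol 27 is that "three or more subjects experience the same serious adverse event as evaluated by a licensed clinician".

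SAP 9.1 says "AEs will be considered treatment-emergent if their onset occurs within the on-therapy period". SAP 5.5 starts that period at the treatment date. SAP Appendix 1 classes an event with a known start date before dosing as not treatment-emergent.

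No visible text says whether increased radicular pain is to be recorded as an adverse event.

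**The concern.** The condition in 23.5.1 is joint: both the character and the severity of the pre-existing condition must worsen. Every patient enters with such a condition, since inclusion criterion 3 requires a mean worst daily leg pain of 5.0 to 9.0. Pain that rises after the injection in the same leg and with the same quality is worse in severity only. So is existing insomnia or low mood that a corticosteroid aggravates; Protocol 12 lists insomnia and depression among the known steroid effects.

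This is a first-in-human study. Safety is a primary objective, and the incidence of TEAEs and serious events is one of its three listed safety endpoints. If some sites follow 23.5.1 to the letter and others follow 26.1, the counts depend partly on which section the site had in mind. With arms this small, a few events classified differently can change the descriptive comparison.

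**Working it through.** No figure in the documents tests this point. The plan's power figures concern responder rates and play no part here. The check is mainly a reading of the definitions side by side.

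**1. The two rules compared.**

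| Change in a pre-existing condition | AE under 23.5.1, read literally | AE under 26.1 |
|---|---|---|
| Character and severity both worsen | yes | yes |
| Severity only worsens | no | yes |
| Character only worsens | no | yes |
| Neither worsens | no | no |

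The rules disagree in the two middle rows. Elsewhere the protocol uses the either-or form. Section 23.5.3 requires a detailed neurological examination if either the characteristics or the intensity of the pain changes for the worse. Table 7 calls a reaction unexpected if it is one "the nature or severity of which is not consistent with the Reference Safety Information". Neither is a rule for what counts as an adverse event, so they show drafting practice and no more.

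**2. What follows from a no.** Serious events (Table 7) and TEAEs (Protocol 31.7) are subsets of adverse events. An occurrence that fails the 23.5.1 test enters neither count, and cannot contribute to the suspension reason based on three patients with the same serious event.

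**3. The SAP's treatment of a worsened condition.** There are three cases:
- not entered as an adverse event: not counted;
- entered with the date of worsening as its start: a TEAE under SAP 9.1;
- entered with its pre-dose start date: not a TEAE under Appendix 1.

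Only the second case is counted, and neither document tells the site to use the date of worsening.

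**4. Size per missed patient.** SAP 3.1 gives 55 treated. Arm sizes are not stated; 1:1:1 allocation suggests 18, 18 and 19, which is an assumption. One patient whose only event is missed lowers that arm's incidence by 1/18 = 5.6 or 1/19 = 5.3 percentage points.

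**5. Illustration for the suspension reason.** The documents give no serious event rate, so rates r of 1%, 2% and 5% for one particular serious event are assumed. With n = 55, the probability of three or more cases is 1 − Σ(k=0..2) C(55,k) r^k (1−r)^(55−k). If only half the cases are recorded, r is replaced by r/2.

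| Assumed r | All recorded | Half recorded |
|---|---|---|
| 1% | 1.8% | 0.3% |
| 2% | 9.8% | 1.8% |
| 5% | 52.3% | 15.9% |

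Incomplete recording would matter for this reason, but how much depends entirely on the assumed rate and on the assumed half.

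**The case against.** The strongest reply is that a reader might infer that severity-only worsening is certain to vanish, and that the documents do not support this. The phrase in 23.5.1 is loose and the section refers onward to Section 26. The definition there is broad, and doubtful observations are to be reported. Two sections in conflict are themselves a source of doubt, and 23.5.1's own description of resolution fits worsening from the pre-treatment state being an event. This stands. Some sites will report such events, so the defect is a conflict with a risk of omission and uneven recording.

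Nor is the suspension rule disabled as a whole. The reasons in Protocol 27 are expressly not exhaustive. One concerns laboratory values, and another covers a pattern of symptomatic or clinical events as judged by the Safety Review Committee, with no restriction to adverse events. SAP 3.4 places the halting criteria in a charter that is not among the documents. Only the reason based on identical serious events is exposed.

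A reader might also infer that every admission for worse pain is excluded. The hospital wording in 23.5.1 concerns planned treatment, and an unplanned admission is not that. The underlying condition could still be held to fail the joint test, so some ambiguity remains.

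Finally, worse leg pain is still captured by the daily diary, the global impression of change and the Oswestry index, whatever its status as an adverse event. This too stands, so a true excess would not be invisible. But these are efficacy records and are not part of the adverse event tables, and under Protocol 23.1 the pain diary stops for a patient who needs treatment beyond rescue.

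The visit procedures and the end of 23.1 are redacted, so site instructions on this matter cannot be ruled out.

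**Conclusion.** The point holds as a conflict between Protocol 23.5.1 and 26.1 that the SAP leaves in place. On the literal rule, severity-only worsening is misclassified, and in practice it may be left out or recorded inconsistently. The exposed outputs are the TEAE and serious event counts and the suspension reason based on three patients with the same serious event. The other suspension reasons and the efficacy records of pain are not affected.

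The number of events lost cannot be derived from the documents. The 5.3 to 5.6 points per missed patient rests on near-equal arms and on that patient having no other event. A reader might go further and infer a bias toward no difference between SX600 and placebo. That would require more severity-only worsening on active treatment and literal use of 23.5.1 at the sites, and the documents establish neither. The change is worth making because the counts bear on a primary objective and the correction is cheap.

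**What to change.** 1. Protocol 23.5.1: replace the joint condition by an either-or condition, so that worsening in nature or in severity makes a pre-existing condition an adverse event, in line with 26.1. State that the date of worsening is recorded as the onset date.
2. SAP 9.1 and Appendix 1: define a TEAE as an adverse event with onset, or worsening of a pre-existing condition, on or after the treatment procedure.
3. Before database lock, run one query of medical-history changes (Protocol 23.5.2) and concomitant medications and therapies (Protocol 23.5.5; SAP 6.6 and 6.7) for worsened conditions not entered as adverse events. It should be run and resolved by staff with no access to treatment allocation.

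Enrolment has stopped, so the protocol wording can only affect follow-up still to come; the SAP change and the query carry most of the value. The cost is a short text change in each document, with ethics committee approval for the protocol amendment (Protocol 28.1), and some query work. The downside is somewhat higher adverse event counts in all arms. The sample size and the efficacy analyses do not change.
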